4.2.4 Impact of COVID-19

The FDA and European Medicines Agency (EMA) have provided guidance (see references listed in [Section 12](#)) to help assure the safety of all trial participants, maintaining compliance with good clinical practice (GCP), and minimizing risks to trial integrity during the COVID-19 pandemic.

At the time of writing this SAP, the impact of the pandemic is still evolving and regulators continue to clarify their position, and how to handle missing or delayed assessments resulting from the pandemic is part of the risk assessment of the impact of COVID-19 on trial integrity.

For this purpose, the impact at a visit level will be assessed by data collected on a specific COVID-19 impact eCRF form and protocol deviations related to COVID-19. Due to the timing

of the start-up of recruitment of participants into this study, the consequences for Part B are not expected to be significant and, as a result, no details on strategies for handling missing data are included in this version of the SAP. However, should the ongoing review of COVID-19-related protocol deviations suggest that the impact is more significant than expected, e.g. in the case of a new wave, the SAP may be updated to include further details of handling missing data and/or any sensitivity analyses required. Note that there are no guidelines regarding how much missing data is too much, and there is no proportion of missing data under which valid results and preservation of study power can be guaranteed. In accordance with the EMA guidance, an independent Data Monitoring Committee (DMC) may be convened to make an assessment regarding the scientific integrity of the study.

4.3 Handling of repeated and unscheduled measurements

All repeated and unscheduled measurements will be presented in the data listings, where applicable. Repeated measurements are defined as more than 1 measurement at the same timepoint. For example, the same laboratory parameters assessed twice using the same batch of blood samples due to issues with the first assessment. The following general rules will apply to all repeated and unscheduled measurements:

- Unscheduled and repeated measurements prior to the first dose of UCB6114 will be used in the determination of Baseline and hence in the calculation of summary statistics at Baseline;
- Unscheduled and repeated measurements performed after the first dose of UCB6114 will not be included in the calculation of change from Baseline, summary measures such as minimum, maximum, average and last post-Baseline value calculated for the summaries of laboratory data (see [Section 8.3](#)), vital signs (see [Section 8.4.1](#)) and 12-lead ECG (see [Section 8.4.2](#)), or summary statistics, i.e. only the scheduled measurements will be used and summarized. Similarly, only scheduled visits will be used in the summaries of shifts from Baseline to the worst post-Baseline CTCAE severity grade for laboratory data (see [Section 8.3](#));
- For the summaries of the investigator's overall tumor response assessment, protocol-defined windows will be applied to all post-Baseline tumor assessments (scheduled or unscheduled, but excluding tumor assessments performed at the SFU visit), as detailed in [Section 10.1.2](#). Those tumor assessments which fall outside of the window will be considered as unscheduled assessments and not included in the summaries;
- Best overall response, DOR and PFS derivations will use data from all scheduled and unscheduled tumor assessments.;
- All data from unscheduled visits will, however, be included on the relevant data listings.

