3.3 Definition of Baseline values

Baseline in Part B will be the last available value prior to the first dose of UCB6114. Both scheduled and unscheduled values, as well as any repeated values, should be used when defining Baseline.

Measurement-specific Baseline definitions are presented in [Table 3-1](#).

Table 3-1: Definition of Baseline

Measurement	Definition of Baseline
Echocardiogram (LVEF) Tumor assessments (antitumor activity)	Screening value
12-lead ECG Physical examination and weight Vital signs Clinical laboratory data ECOG performance status	Predose value obtained on Cycle 1, Day 1, or, if missing, Screening value
Serum and urinary markers of bone turnover Circulating gremlin-1 (cGremlin-1) Immunogenicity (ADA)	Predose sample value obtained on Cycle 1, Day 1

ADA=anti-drug (UCB6114) antibody; ECG=electrocardiogram; ECOG=Eastern Cooperative Oncology Group; LVEF=left ventricular ejection fraction.

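### Section 4.3 drops a post-Baseline laboratory re-assay from the summaries even when it was made because the first result had a problem, while before dosing the same kind of repeat counts towards Baseline

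*SAP*

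**What the plan says.** Section 4.3 appears with the same rules in both SAPs. It defines the term: "Repeated measurements are defined as more than 1 measurement at the same timepoint". The one example given is "the same laboratory parameters assessed twice using the same batch of blood samples due to issues with the first assessment". The section then sets general rules covering repeats and unscheduled measurements together.

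- **Before first dose:** "Unscheduled and repeated measurements prior to the first dose of UCB6114 will be used in the determination of Baseline". Section 3.3 agrees; Baseline is the last available predose value, and "Both scheduled and unscheduled values, as well as any repeated values, should be used when defining Baseline".
- **After first dose:** "Unscheduled and repeated measurements performed after the first dose of UCB6114 will not be included in the calculation of change from Baseline". The same exclusion covers the minimum, maximum, average and last post-Baseline value for laboratory data, vital signs and ECG, and the summary statistics, so that "only the scheduled measurements will be used and summarized".
- **Worst-grade laboratory shifts:** "only scheduled visits will be used in the summaries of shifts from Baseline to the worst post-Baseline CTCAE severity grade for laboratory data".
- **Listings:** all repeated and unscheduled measurements are listed.

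Sections 8.3 (laboratory), 8.4.1 (vital signs) and 8.4.2 (ECG) likewise base the per-cycle measures on scheduled values. No section says that a corrective repeat replaces the first result, that such a first result is set to missing, or which of two results at one timepoint is the scheduled one.

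**The concern.** A repeat and an unscheduled measurement are different things. An unscheduled visit adds an observation, often because something looked abnormal, and leaving it out of by-visit summaries is reasonable. A re-assay of a sample already drawn at a scheduled timepoint adds no visit; it offers a second result for the same planned observation. In the SAP's own example the second result exists because the first was in doubt.

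Putting both under one exclusion makes the post-dose rule work against its own example: the better result is set aside. Because the pre-dose rule goes the other way, a change from Baseline can subtract a corrected Baseline from an uncorrected post-Baseline value. At stake is the accuracy of descriptive safety tables in dose groups small enough for one wrong value to show.

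**Working it through.** The SAP gives no figure to reproduce here. The check is to run the SAP's own example through its rules and then scale the effect.

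**Step 1: the example, before and after first dose.** A scheduled sample is assayed, the assay has a problem, and the same sample is assayed again.

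| | Before first dose | After first dose |
|---|---|---|
| Repeat eligible for analysis? | Yes (3.3, 4.3) | No (4.3) |
| Value used | Last available, so the re-assay | Scheduled measurement only; on the natural reading, the first result |
| If the first result is voided | Re-assay still available | Nothing is left: the re-assay is excluded, and 4.2 allows no imputation unless stated |

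After first dose, then, either the doubtful value is summarised or a valid value is lost.

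**Step 2: visit mean.** Let the retained first result carry error d, with n participants contributing at that visit. The mean, and the mean change from Baseline, shifts by d/n. Section 2.3 gives 3 to 9 evaluable participants per dose level. Taking that range as an assumption for n:

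- n = 3: d/3
- n = 9: d/9

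The true n may differ. Section 8 bases these tables on the Safety Analysis Set, which includes replaced participants, and section 3.1 counts only those with non-missing data at the visit.

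**Step 3: cycle minimum and maximum.** Changing one value by d changes the maximum or minimum of a set by at most d, and often by less. Illustration with invented values: the other two results are 5 and 7, the true third is 6, and the error is +3, so 9 is recorded. The maximum goes from 7 to 9, a move of 2, and the minimum stays at 5.

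**Step 4: ECG.** Section 8.4.2 summarises the mean of a triplicate. With all three tracings present, one faulty tracing with error d enters as d/3 before any averaging over participants.

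**Step 5: worst-grade CTCAE shift.** The restriction is worded by visit, not by measurement, so a re-assay at a scheduled visit is not expressly barred. There are two readings:

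- The opening word of that sentence carries over the exclusion of repeats: only the first result is graded.
- Both results at the visit are eligible: the worst grade is taken, so a faulty first value still sets it whenever it is the more extreme.

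On either reading a faulty first value can determine the tabulated grade. One misgraded participant is 1/3 = 33.3% of a group of 3 and 1/9 = 11.1% of a group of 9, under the same assumption on n.

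**The case against.** The case for leaving the text alone has several parts.

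- **The convention is common.** Using the last predose value as Baseline and scheduled values afterwards is prespecified and stops result-driven retesting from shaping the summaries. This stands for unscheduled visits. It does not justify excluding a corrective re-assay at a scheduled timepoint.
- **The re-assay is only an example.** Not every repeat implies a wrong first value, and a problem with an assay may mean that it gave no number at all. This stands. A reader might infer that post-Baseline summaries are in general built on values known to be faulty; the SAP does not support that. The point applies only to corrective repeats, and its other branch is a missing value.
- **Data cleaning would remove a bad result.** The SAP states no such rule, and if the result were removed, the valid repeat would remain excluded.
- **The repeat could be taken as the scheduled value.** The text does not say so, and it excludes repeats by name.
- **Nothing is hidden.** A reader might infer that a true abnormality seen on a repeat disappears. It does not: section 4.3 lists every repeat, and section 8.3 adds a listing of laboratory results outside the reference range. Only the tables are affected.
- **The primary endpoints are safe.** This stands. TEAEs and DLTs (2.2.1.1, 8.2) come from investigator-recorded events, not from these tables, so no effect on dose-escalation decisions can be read into the point.
- **Vital signs and ECG are not shown to be at risk.** Largely so. The exclusion covers them, but the only corrective repeat described is a laboratory one.

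The SAP already handles a similar conflict sensibly elsewhere: in section 10.1.2, when two tumor assessments fall in one window and one is not evaluable, the other is used.

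**Conclusion.** The point holds in a limited form. Section 4.3 of both SAPs excludes post-Baseline repeats under a rule suited to unscheduled visits, and in its own example that rule gives the worse result. This is a stated rule that works badly, not a missing detail.

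The conclusion rests on reading the first result as the scheduled one, which is natural but not stated. The consequence is confined to descriptive safety summaries, chiefly laboratory. Per faulty value with error d, a visit mean shifts by d/n and a cycle extreme by no more than d; the worst-grade shift is affected when the faulty value is the more extreme, or when it alone is graded. The range 3 to 9 for n is borrowed from the evaluable count per dose level. How often corrective repeats occur is not given, so the total effect cannot be estimated. It is worth correcting because the groups are small and safety is the primary objective, but it does not threaten the TEAE or DLT results.

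**What to change.** In section 4.3 of both SAPs, separate repeats from unscheduled measurements and state:

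1. Where a scheduled assessment is repeated at the same timepoint because of a documented problem with the first result, the valid repeat replaces it in summaries, changes from Baseline, per-cycle measures and CTCAE shift tables. The first result is listed and flagged.
2. Where no problem is documented, the first result is kept.
3. Unscheduled visits stay excluded as now.

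The documented-problem condition, fixed before database lock, also prevents choosing between two results after seeing them. The cost is a few sentences in each SAP and a derivation flag. The one dependency is a recorded reason for each repeat; the SAP does not show whether the eCRF or the local laboratory data hold it, so this should be checked first.

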2.2 Study endpoints

2.2.1 Safety endpoints

2.2.1.1 Primary safety endpoints

The primary safety endpoints for Part B of this study are the incidence and severity of treatment-emergent adverse events (TEAEs) (including serious adverse events [SAEs]) from the first dose of UCB6114 on Day 1 of Cycle 1 to the Safety Follow-up (SFU) visit, and the incidence of dose limiting toxicities (DLTs) from the first dose of UCB6114 on Day 1 of Cycle 1 to the end of the DLT Observation Period (Day 28 of Cycle 1).

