Part B will be undertaken using the modified toxicity probability interval (mTPI) method. The mTPI design uses a Bayesian decision framework to inform dose-escalation and dose de-escalation decisions. A target DLT rate of 25% with an equivalence interval (20% to 30%) will be used to estimate the maximum tolerated dose (MTD) of the combination regimen during dose escalation. For all UCB6114 dose levels, enrolled participants will be treated in cohorts of 2 to 4 participants (target of 3), who can be treated in parallel. Each UCB6114 dose level may have more than one cohort and will have a minimum of 3 and a maximum of 9 evaluable participants. For further detail on the mTPI method, the calculated model-based dose-escalation/dose de-escalation decisions to help inform the Safety Monitoring Committee (SMC)'s decision, and the determination of the MTD, please refer to Section 4.1.3.2.2 of the protocol. Detail on the operating characteristics for the mTPI design is included in [Section 2.4](#) below.

[figure not shown]
The planned duration of study treatment during Part B is 2 cycles. Participants may remain on study for additional cycles if they are receiving therapeutic benefit or until they fulfill one of the criteria for study discontinuation. Participants will continue treatment until disease progression, unmanageable toxicity, or withdrawal of consent. Upon discontinuation of treatment, participants will be referred to appropriate follow-up care per the investigator's judgment.

From Part B, a recommended Phase 2 dose for UCB6114 in combination with TFD/TPI (RP2D-T) will be determined based upon the totality of information, including the safety profile, PK data, PD biomarker data, and available antitumor activity.

Part B of the study is planned to be conducted at study sites in the United Kingdom (UK) and United States (US).

A schematic diagram of Part B of the study is provided in [Figure 2-1](#).

Figure 2-1: Study Schematic for Part B

bid=twice daily; D=Day; DLT=dose-limiting toxicity; iv=intravenous; mTPI= modified toxicity probability interval; po=oral; TFD/TPI=trifluridine/tipiracil

*Dose must not exceed 80mg/dose

Notes: A dose may be given in more than 1 cohort

Escalation to the next dose level or de-escalation to the previous dose level will be guided by the mTPI algorithm.

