3.2.3 Study periods

Part B of the study will consist of the following study periods:

- Screening Period – up to 28 days;
- Treatment Period – Successive 28-day cycles of study treatment (UCB6114 will be administered as an iv Q2W dose on Day 1 and Day 15 of each cycle and TFD/TPI will be

administered [bid] within 1 hour of completion of morning and evening meals at home on Days 1 to 5 and Days 8 to 12, continuing until disease progression, unmanageable toxicity, or participant withdrawal). Within the first cycle of the Treatment Period, a 28-day DLT Observation Period is defined to determine safety events for dose escalation decisions using mTPI;

- Safety Follow-up Period – up to 30 days after the last dose of UCB6114.

There will be a further extended follow-up period, up to 3 months after the last dose of UCB6114, at which time the Final Visit will be performed.

For each participant, the end of the Treatment Period is defined by the date of their last dose of UCB6114.

The end of Part B of the study is defined by the date of the Final Visit for the last participant (3 months after the last participant's last dose of UCB6114), or the date of the SFU visit, if they discontinue prior to attending the Final Visit, or their last contact date if they discontinue early from the study without attending the SFU visit.

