8.2 Adverse events

The primary safety endpoints for Part B of this study are the incidence and severity of TEAEs (including SAEs) from the first dose of UCB6114 treatment on Day 1 of Cycle 1 until the end of the SFU Period (up to 30 days following the last dose of UCB6114 treatment), and the incidence of DLTs from the first dose of UCB6114 on Day 1 of Cycle 1 until the end of the 28-day DLT Observation Period (Day 28 of Cycle 1).

All AEs in Part B of the study will be coded using MedDRA® and classified as pre-treatment and treatment-emergent relative to the first dose of UCB6114 treatment. Adverse events with a start date prior to the first infusion of UCB6114 will be defined as pre-treatment AEs. A TEAE is defined as any AE with a start date on or after the first dose of UCB6114 up until the last dose of UCB6114 + 30 days. A pre-treatment AE which increases in severity on or after the first dose of UCB6114 will also be counted as a TEAE. Note that in this case, the pre-existing AE will have a stop date and an outcome of ‘worsened’ and a new AE (with the same verbatim) will be entered with the same start date and the increased severity recorded on the eCRF. Any AE (including SAEs) with an onset date later than the last dose of UCB6114 + 30 days will not be considered as treatment-emergent and therefore will not be included in the tabulations of TEAEs. These AEs will be considered as post-study AEs and will be listed only. Where onset dates are missing or partially missing, AEs will be assumed to be treatment-emergent, unless there is clear evidence to suggest that the AE started prior to the first dose of UCB6114 and it has not increased in severity. Missing or partially missing dates for AEs will be handled as described in [Section 4.2.3](#) All AEs for a participant will be recorded in the eCRF from the time of informed consent until completion or early discontinuation of Part B of this study. Serious adverse events are to be reported up to 30 days after the Final Visit (i.e. up to 150 days after the last dose of study treatment).

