Observed normalized values and changes from Baseline in the hematology, serum chemistry and coagulation parameters presented below in [Table 8-1](#) will be summarized at each visit. In addition, for each of these parameters, the Baseline value, the minimum, maximum, average and last post-Baseline value for each participant will be summarized by cycle using descriptive statistics. These post-Baseline summary measures will be calculated based on all available scheduled postdose values within each cycle, i.e. from Day 8 of the current cycle up to Day 1 (pre-UCB6114) of the subsequent cycle. The last value in a cycle will be the predose value of the subsequent cycle where a subsequent cycle occurs, otherwise it will be the value at the last scheduled assessment. If only one value is available then the average will not be calculated and presented but this value will be used for the minimum, maximum and last post-Baseline summary measures. These summary measures for each cycle will also be listed.

The summaries of normalized hematology, serum chemistry and coagulation values and changes from Baseline will also be presented by Gastric/GEJ-Cancer and CRC tumor type depending on the number of participants with specific tumor types.

For those laboratory parameters with a CTCAE toxicity assigned, shift tables for the change from Baseline in CTCAE severity grade at each visit and to the worst post-Baseline CTCAE severity grade during the Treatment Period will be presented.

Table 8-1: Clinical Laboratory Assessments

Laboratory Assessment	Laboratory Parameters
Hematology	Platelet Count, RBC Count, Hemoglobin, Hematocrit, RBC Indices (MCV, MCH, MCHC), WBC Count with Differential (Absolute Neutrophils, Absolute Lymphocytes, Absolute Monocytes, Absolute Eosinophils, Absolute Basophils)
Clinical Chemistry	ALT, AST, ALP ^a , Bicarbonate, Sodium, Potassium, Magnesium, Chloride, Calcium, Total Bilirubin, BUN or Urea, Serum Creatinine, Glucose (non-fasted), Phosphorus or Phosphate, Albumin, Total Protein, Uric Acid, Amylase, GGT, Cholesterol, Creatine Kinase, CRP, LDH, Lipase, Triglycerides
Coagulation	aPTT and either prothrombin time or INR
Routine Urinalysis	Specific Gravity, pH, Glucose, Protein, Blood, Ketones, Bilirubin, Urobilinogen, Nitrite, Leukocyte Esterase by Dipstick Microscopic Examination (if blood or protein is abnormal, including crystals)

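### In both parts, the worst post-Baseline laboratory CTCAE grade leaves out unscheduled results and, as written, everything after the last UCB6114 dose, so it can only understate severity

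*SAP*

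**What the plan says.** Four rules bear on this point. They read the same way in the Part B and Part C plans.

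- **Which results count.** Section 4.3 states that "only scheduled visits will be used in the summaries of shifts from Baseline to the worst post-Baseline CTCAE severity grade for laboratory data". The same paragraph removes unscheduled and repeat values taken after the first dose from the laboratory minimum, maximum, average and last value. Such results go to the listings.
- **Which period counts.** Section 8.3 promises shifts "to the worst post-Baseline CTCAE severity grade during the Treatment Period will be presented".
- **When that period ends.** Section 3.2.3 says that for each participant "the end of the Treatment Period is defined by the date of their last dose of UCB6114".
- **What the AE tables use.** Section 8.2 defines a TEAE as "any AE with a start date on or after the first dose of UCB6114 up until the last dose of UCB6114 + 30 days".

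Section 8.1 (8.1.1 in Part B) also adds 30 days to the duration of exposure, on the ground that exposure continues after the last dose. In Part C this covers the mFOLFOX6 components as well.

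The by-cycle laboratory measures in Section 8.3 follow another window: from Day 8 up to the predose value of the next cycle. Where no next cycle occurs, the last value is set differently: "otherwise it will be the value at the last scheduled assessment".

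**The concern.** A table headed as the worst post-Baseline grade will be read as the most severe laboratory value that each participant had. Under these rules it is the most severe value in a restricted subset. Unscheduled samples are often drawn because toxicity is suspected or being followed. That is a reasonable inference, though the SAP does not say it. The cut-off at the last dose takes the largest share of follow-up from participants who stop early, and some of them will have stopped for toxicity.

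The SAP's other choices do not support the restriction. It treats the 30 days after the last dose as exposed time and counts AEs in them. Section 4.3 itself uses unscheduled tumor assessments for best overall response, DOR and PFS, and unscheduled laboratory values for Baseline. The worst toxicity grade is thus denied data that the best response receives.

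At stake is the laboratory severity profile of a chemotherapy combination whose primary objective is safety, at dose levels with 3 to 9 evaluable participants.

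**Working it through.** The SAP states no figure for this rule, so there is none to reproduce. The check sets the rules together and counts days on the SAP's own schedule.

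**Step 1, direction.** A maximum over a subset of results is never higher than the maximum over all of them. Leaving out valid results can therefore only leave the worst grade unchanged or lower it.

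**Step 2, inputs.**
- Schedule: "UCB6114 will be administered as an iv Q2W dose on Day 1 and Day 15 of each cycle" (Section 3.2.3), with 28-day cycles.
- Planned length: "The planned duration of study treatment during Part B is 2 cycles" (Section 2.3; Part C also plans 2 cycles of UCB6114), so 4 doses on Days 1, 15, 29 and 43.
- End of the worst-grade window, read literally: day of last dose = 1 + 14 × (doses − 1).
- End of the TEAE window: day of last dose + 30.

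**Step 3, share of the TEAE window left out, literal reading.**

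| Doses | Last dose day | TEAE window ends | Days left out |
|---|---|---|---|
| 1 | 1 | 31 | 30/31 = 97% |
| 2 | 15 | 45 | 30/45 = 67% |
| 3 | 29 | 59 | 30/59 = 51% |
| 4 (planned) | 43 | 73 | 30/73 = 41% |

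All rows assume doses on the nominal days.

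**Step 4, the early stopper.** Section 8.3 starts the postdose laboratory values at Day 8. A participant who stops after Day 1 has a one-day Treatment Period, so no scheduled postdose result falls inside it. Within the 28-day DLT Observation Period, the table cannot use 28 − 1 = 27 days for that participant, or 28 − 15 = 13 days for one who stops after Day 15.

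**Step 5, the looser reading.** Section 3.2.3 also describes the Treatment Period as successive 28-day cycles. If the window ran to the end of the cycle of the last dose, the days left out would be 31 − 28 = 3 of 31 (10%) after one dose, 45 − 28 = 17 of 45 (38%) after two, and 73 − 56 = 17 of 73 (23%) after four. The window would still be shorter than the TEAE window, and the exclusion of unscheduled results would be untouched.

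**Step 6, sensitivity of a small table.** With 9 participants at a dose level, one participant moved to a higher grade changes a percentage by 1/9 = 11 points, and by more with fewer participants. This shows the scale only; it does not predict that such a case will occur.

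**The case against.** The strongest reply is that the table is supportive and that much of the missing information appears elsewhere. Section 2.2.1.1 names TEAEs and DLTs as the primary safety endpoints; laboratory data are other safety data under Section 2.2.1.2. A laboratory abnormality reported as an AE, at whatever kind of visit, enters the TEAE tables by maximum CTCAE grade up to last dose + 30 days. Section 8.3 lists results and grades for participants with any out-of-range value. SFU data enter the by-visit tables (Section 4.4), and grade shifts are shown at each visit. With up to 27 participants per part, reading listings is practical. All of this stands and limits the harm. None of it gives a laboratory-based worst grade per participant.

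The cut-off at the last dose also comes from joining two sections, and Section 3.2.3 describes cycles as well. That is fair, but the only explicit end date for a participant is the last UCB6114 dose, and a programmer would apply it.

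A reader might infer three stronger things that the documents do not support:

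- **That dose escalation or the primary safety analysis is biased.** Escalation decisions use the DLT Evaluable Set and the safety committee's cumulative review (Sections 3.5.7 and 4.5), not this table.
- **That 97% or 41% of toxic results, or some modelled share of blood-count nadirs, are missed.** The shares are of calendar days. The number of tests in those days depends on the protocol's schedule, which is not at hand, and a nadir model would need a duration and timing that the SAP does not give.
- **That the potential drug-induced liver injury (PDILI) and liver-multiple counts are cut in the same way.** Section 8.3 defines the PDILI criteria at a visit and summarises the liver multiples by visit, and Section 4.3 does not name either.

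**Conclusion.** The point holds for one supportive table in each part and, as regards unscheduled values, for the by-cycle minimum and maximum. The exclusion of unscheduled results is stated outright. The exclusion after the last dose, including SFU, rests on the literal definition of the Treatment Period. The direction is certain: the worst grade is equal or understated, never overstated.

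The size in grades or participants cannot be computed, because the SAP contains no laboratory data. That the omitted results are especially likely to be severe is plausible but not shown. This should be corrected before the tables are run, but it does not put the primary safety endpoints in doubt.

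**What to change.** In Sections 4.3 and 8.3 of both parts:

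1. Derive the worst post-Baseline laboratory CTCAE grade from all valid scheduled and unscheduled results after the first UCB6114 dose up to the last UCB6114 dose + 30 days, the window already used for TEAEs.
2. State that a repeat made because of a faulty assay replaces the faulty value. Section 4.3 gives this very example of a repeat, so admitting every repeat could let an invalid result set the grade.
3. Include valid unscheduled results in the by-cycle minimum and maximum, and keep the by-cycle windows of Section 8.3.
4. Keep by-visit summaries and by-visit grade shifts on scheduled data.

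The PDILI and liver-multiple counts need no change on this account.

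No new data are needed: unscheduled results are already listed, and CTCAE grades are already derived in the ADaM programming. The cost is SAP wording, an analysis flag and slightly more programming. Counts of higher grades may rise, and the table title or footnote should state the window so that readers know what it covers.
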